3. OBJECTIVES AND OUTCOME MEASURES

3.1 Primary objective

Does doxycycline given prior to conception improve the number of on-going pregnancies and total live births in women with recurrent miscarriage associated with chronic endometritis?

3.1.1 Primary outcome measures

This trial will use an adaptive design methodology so that we can stop the trial early in the case of better than expected efficacy or futility. Therefore we need two primary outcome measures. One that is reached earlier than the whole 40 weeks of pregnancy. Hence, one explanatory, primary outcome measure will be ongoing pregnancy.

3.1.2 Primary Outcome 1

The first explanatory primary outcome measure will be on-going pregnancy at 12 weeks. Ongoing pregnancy is defined as the number of viable pregnancies, with a crown rump length >54 mm, reaching 12+6 weeks of gestation as a percentage of the total number of first pregnancies after the intervention. As 98% of miscarriages occur before 12 weeks, the number of ongoing pregnancies will be very similar to number of live births.

3.1.3 Primary Outcome 2

The second pragmatic primary outcome measure will be the total live births defined as total live births plus ongoing pregnancies at the end of trial. Defined as: On-going pregnancy at 12+6 weeks gestation

the presence of a fetal heart beat when the Crown Rump Length >54mm

total number of women randomised

- Total live births = Projected live births >24 weeks in first or subsequent pregnancy analysed at the end of the trial as proportion of women (whilst some babies born at 22 and 23 of weeks of gestation survive, they are at risk of long term disability and hence will not be included in this outcome measure).
- The maximum denominator for both of these analyses will be the 1,500 women randomised. This change does not affect any of our simulations for likelihood of early stopping.

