12.1.3 Sample size - randomised controlled trial

The target sample size is 1,500, 750 women in the intervention arm (doxycycline) and 750 women in the control arm (placebo).

The total number of women recruited to the screening part of trial will be determined by the proportion eligible for the randomised controlled trial. Our current assumptions suggest as overall recruitment of around 3,062 women over 24 months with 1,500 women in the randomised trial.

In simulations, we have used a maximum sample size of 1,500, and a maximum recruitment rate of 16 women/week from all centres. We have used four interim analyses, after 250, 500, 750 and 1000 women have been recruited, with the following stopping rules: stopping for futility/harm if the predictive probability of obtaining p<0.025 if the trial continued to its full sample size is less than 0.01, and stopping for established efficacy if the probability that the intervention is better than control is greater than 0.99. We assumed that 24% of women would get pregnant every month, giving an overall proportion achieving pregnancy by six months of 80%, and that the 12-week outcome would be known between 16 and 36 weeks after randomisation. The performance of this design was good in two treatment effect scenarios. With no difference between the intervention and control groups, 71.4% of trials stopped early for futility (correctly), and 1.2% stopped early for success (Type I error). The average sample size was 1193, and the average duration was 130 weeks (recruitment and follow-up). With the target treatment effect (48% control, 56% intervention), 54.8% stopped early for success, and an additional 33.4% did not stop early but found probability of benefit to the intervention group of >95%, giving an overall probability of correctly identifying benefit (power) of 88.2%. Average sample size was 1,247 and duration was 133 weeks.

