12.3 Statistical analysis

The primary analysis will be conducted by intention to treat (ITT). The treatment difference will be compared between the participants randomised to placebo and doxycycline. The primary outcomes, on-going pregnancy at 12 weeks and total live births, will be analysed using logistic regression models.

Secondary analysis will be conducted in a similar approach. The treatment effect will be compared to assess the categorical and continuous secondary outcomes using logistic and linear models, respectively.

Mediation analysis will be carried out to investigate whether any treatment effect on the total number of live births is mediated by conception, early miscarriage, or late miscarriage.

The results will be reported as odds ratio (OR) with 95% confidence interval (CI) for categorical outcomes and mean difference with 95% CI for continuous outcomes. The analysis will be conducted in an unadjusted and adjusted way, with adjustment for the stratification variables and important covariates. Missing data for the primary outcomes are likely to be minor. However, if the missing primary outcome data exceeds 20%, imputation techniques will be employed and the imputed data will be used as a sensitivity analysis.

Treatment effect will also be assessed in the following subgroup for exploratory purpose:

- Age (<35 vs ≥35)
- Severity of chronic Endometritis:
 - Negative (0-4 CD138 cells)
 - o Mild (5-20 CD138 cells)
 - Moderate (21-200 CD138 cells)
 - Very high (201+ CD138 cells)
- number of previous miscarriages (≤3 vs >3)

The interaction between the subgroup variable with treatment will be tested and the overall significance of the interaction will be reported.

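### Primary outcome 1 has two denominators, first pregnancies in 3.1.2 and women randomised in 3.1.3, and the protocol does not say which one the 48% and 56% use

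*Protocol*

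**What the plan says.** Section 3.1.2 counts viable pregnancies "reaching 12+6 weeks of gestation as a percentage of the total number of first pregnancies after the intervention". Section 3.1.3, under primary outcome 2, defines on-going pregnancy at 12+6 weeks again, this time over the "total number of women randomised". It adds: "The maximum denominator for both of these analyses will be the 1,500 women randomised". It then remarks: "This change does not affect any of our simulations for likelihood of early stopping". Section 4 places the outcome in the first pregnancy after randomisation but names no denominator.

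Section 12.3 makes the primary analysis intention to treat and specifies the model: "The primary outcomes, on-going pregnancy at 12 weeks and total live births, will be analysed using logistic regression models". Sections 12.1.3 and 12.3.1 give the target effect without a denominator: "With the target treatment effect (48% control, 56% intervention), 54.8% stopped early for success". They put overall power at 88.2%. Section 12.3.1 uses on-going pregnancy for the interim analyses after 250, 500, 750 and 1,000 women.

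**The concern.** Both definitions stand in current text, so an analysis could follow either and claim to comply with the protocol. They answer different questions. The per-woman version compares the randomised groups. The per-pregnancy version compares only women who conceived, and conception happens after randomisation. The protocol treats conception as something doxycycline may change: its effect on conception is a secondary objective (3.2), section 4 mentions possible effects on fertility, and section 12.3 plans a mediation analysis through conception. If treatment changes who conceives, the per-pregnancy comparison is biased.

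At stake are the efficacy and futility decisions at four interim looks, and the meaning of the stated power.

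**Working it through.** **1. How many women the denominators separate.** Sections 12.1.3 and 12.3.1 assume 24% conceive per month, about 80% by six months: 1 − 0.76^6 = 0.807. At 80%, 1,500 × 0.20 = 300 randomised women leave the per-pregnancy analysis. Section 3.1.2 sets no six-month limit, and section 7.11 follows women for 14 months after the last randomisation. Assuming 24% per month stays constant for 11 months (14 less about three to reach 12+6 weeks), 1 − 0.76^11 = 0.951, and about 73 women leave. The gap is therefore roughly 73 to 300 women, depending on the window.

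**2. Whether the versions can disagree.** Per-woman rate = conception rate × success per pregnancy. All rates here are assumed, for illustration only.

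| Conception, control vs doxycycline | Per pregnancy | Per woman |
|---|---|---|
| 80% vs 72% | 60.0% vs 66.7% | 48.0% vs 48.0% |
| 75% vs 85% | 60% vs 60% | 45% vs 51% |

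The first row shows a 6.7-point gain per pregnancy and none per woman. The second shows no difference per pregnancy and 6 points per woman. If conception is equal in both arms and treatment does not alter who conceives, the two versions agree in direction.

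**3. Which denominator reproduces 88.2%.** Fixed-design power, 1:1, n per arm:

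power = Φ[(d − z × √(2p̄(1−p̄)/n)) / √((p0(1−p0) + p1(1−p1))/n)], where d = p1 − p0 and p̄ is the mean of p0 and p1.

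For 48% vs 56% and n = 750, the two standard errors are 0.02580 and 0.02572:
- one-sided 0.025: (0.08 − 1.960 × 0.02580)/0.02572 = 1.14, power 87.4%
- one-sided 0.05: (0.08 − 1.645 × 0.02580)/0.02572 = 1.46, power 92.8%

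For n = 600 (80% of 750 conceiving), they are 0.02884 and 0.02875:
- one-sided 0.05: power 87.1%
- one-sided 0.025: power 79.3%

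So 88.2% is matched about equally well by 750 women per arm at one-sided 0.025 and by 600 pregnancies per arm at one-sided 0.05. The protocol supports either threshold: its power figure counts a final probability of benefit above 95%, while its futility rule refers to p<0.025.

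A simulation of the stated stopping rules agrees. At the 95% threshold it gives 85–88% for the per-pregnancy reading and 92–93% for the per-woman reading; at 0.025 the per-woman reading gives 87–89%. The stated 54.8% stopping early for success does not discriminate either. Depending on how interim timing is modelled, the simulated share is about 35–64% per pregnancy and 47–69% per woman. The prior, the accrual ramp and the handling of women without a pregnancy are not given, so only overall power was matched.

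**4. What follows if 48%/56% are per pregnancy.** With 80% conceiving in both arms, the per-woman rates are 0.80 × 48% = 38.4% and 0.80 × 56% = 44.8%. At 750 per arm, power is 80.8% (one-sided 0.05) or 71.1% (one-sided 0.025); simulated, 81–83% and 72–75%. Using 80.7% conceiving, 88.2% power without interim looks would need about 934 or 1,154 per arm. With a window long enough for 95% to conceive, the rates are 45.6% vs 53.2%, and the same formula gives 90.4% or 83.8%.

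**The case against.** The strongest reply is that the protocol has already settled the matter. Section 3.1.3 covers both analyses, its reference to a change suggests that the denominator was revised and 3.1.2 missed, and section 12.3 specifies intention to treat. That is the likeliest reading. A reader might infer that a non-randomised comparison is actually planned; the documents do not support that, since the conflict with section 12.3 arises only if the 3.1.2 clause governs. But the clause is still current text, and the word maximum in 3.1.3 does not turn it into a per-woman definition.

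A reader might also infer that 48% and 56% are per-woman rates, being 80% × 60% and 80% × 70%, so that the per-woman wording already matches the sample size. The arithmetic works, but the protocol gives neither 60% nor 70% as a success rate for this outcome, and its power figure fits both readings. The remark that the simulations are unaffected points towards per woman, but it is an assertion and no working is shown.

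It is also fair to say that the second primary outcome is per woman and would capture a fertility effect. That does not protect the interim decisions, which rest on on-going pregnancy.

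**Conclusion.** The contradiction stands and must be resolved in the protocol, because it concerns the primary outcome that governs early stopping. The per-pregnancy version would not be an intention-to-treat comparison, and it is biased if treatment changes who conceives. The protocol raises that possibility but does not establish it, and the discordant examples above rest on assumed rates.

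The effect on power depends on an unstated fact. If 48%/56% are per woman, the design stands. If they are per pregnancy and 80% conceive equally in both arms, fixed-design power for the per-woman outcome is about 81% or 71%, depending on the threshold, rather than 88.2%. A longer window would narrow that loss.

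**What to change.** - In 3.1.2, replace "as a percentage of the total number of first pregnancies after the intervention" with a percentage of the "total number of women randomised". Count a woman without a qualifying on-going first pregnancy as a non-event once a pre-stated follow-up window has passed.
- At interims, use only women who have reached that window or have a known outcome, so that recently randomised women are not scored as failures. Section 12.1.3 assumes outcomes become known 16 to 36 weeks after randomisation. Known on-going pregnancies or losses before the window closes come only from women who conceived, so the plan should say how that is handled; restricting to women past the window is the simpler choice.
- Keep the per-pregnancy percentage as a labelled supportive analysis.
- In section 12, state which denominator 48% and 56% refer to. If it is pregnancies, re-run the simulations per woman and restate the power.

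The wording change is small and follows 3.1.3 and 12.3. The cost becomes material only if the target rates prove to be per pregnancy, since the simulations, and possibly the sample size, would then need revisiting.

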3.2 Secondary objectives

1. To find out if doxycycline treatment improves CE?

2. To examine the separate effects of doxycycline on conception, early miscarriage, and late miscarriage. In addition, assess the mediation effect of each of these, on the primary outcome, with treatment effect as a covariate.

3.2.1 Secondary Outcome measures:

• Density of CD138+ cells in the endometrium before and after treatment

- Time to first conception
- Anticipated time to first live birth
- Live births, the proportion of women with a live birth after 24 weeks of gestation in their first pregnancy after randomisation.
- Pregnancy complications, in first pregnancy following randomisation lasting greater than 12 weeks; second trimester miscarriage, intrauterine death, preterm delivery, small for gestational age and placental abruption..
- Early pregnancy complications (e.g. ectopic pregnancy, molar pregnancy).
- Type of miscarriage, biochemical¹, gestational sac², fetal³, karyotype of miscarried tissue.
- A re-assessment of the ability of the CD138+ cell test to detect which patients will benefit from Doxycycline will be undertaken. This analysis will use on-going pregnancy and live births per patient in women excluded from randomisation by having low CD138+ cell scores and those randomised to placebo.
- Termination for social reasons

¹ Biochemical – Positive pregnancy test without ultrasound visualisation of pregnancy

² Gestational Sac – Presence of gestational sac on ultrasound without visualisation of fetus

³Fetal – Presence of fetus on ultrasound with no fetal heart beating

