7.9 Follow up for women who screen negative for CE

If the results indicate that a woman does not have CE she will not be eligible to participate in the RCT. Women will be contacted to inform them of the results. Women will then be followed-up every 3 months to collect details of any confirmed first pregnancies conceived within 12 months from receiving the result of the endometrial biopsy until delivery or miscarriage. We will collect data on the gestation and pregnancy outcome only i.e. miscarriage, live birth, stillbirth.

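### The CD138 re-assessment compares two groups that get no trial doxycycline, so it can show prognosis but not who benefits; its pregnancy window is unmatched, and a separate subgroup lists an empty level

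*Protocol*

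**What the plan says.** **Purpose and groups.** Section 3.2.1 gives the aim as "A re-assessment of the ability of the CD138+ cell test to detect which patients will benefit from Doxycycline will be undertaken" and names the data: "This analysis will use on-going pregnancy and live births per patient in women excluded from randomisation by having low CD138+ cell scores", together with women randomised to placebo. The doxycycline arm is not mentioned. The outcome table in the Trial Summary lists the same two groups, without the statement about benefit.

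**Follow-up of screen-negative women.** Under section 7.9, sites "collect details of any confirmed first pregnancies conceived within 12 months from receiving the result of the endometrial biopsy until delivery or miscarriage". The data items are few: "We will collect data on the gestation and pregnancy outcome only i.e. miscarriage, live birth, stillbirth". Section 9.5.1 ends contact at 12 months after the result if no pregnancy is reported.

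**Follow-up of randomised women.** The Trial Summary keeps a woman in the trial after a loss before 24 weeks and records her later pregnancies. Section 9.5.2 runs three-monthly contact from treatment completion until 6-8 weeks after a pregnancy of more than 24 weeks, or trial end. Section 7.11 adds 14 months after the last randomisation. Total live births in section 3.1.3 count a first or a later pregnancy.

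**Subgroup.** Section 12.3 plans exploratory treatment effects, with interaction tests, by severity of chronic endometritis. The first level is "Negative (0-4 CD138 cells". Section 6.3 admits to the randomised trial only women with at least 5 CD138+ cells per 10 mm².

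**The concern.** Whether a test identifies who benefits from a drug is a question about how the drug's effect changes with the test result. Answering it needs treated and untreated women at different test values. Section 3.2.1 names two untreated groups, and no later analysis plan can extract a treatment effect from them. Section 17 expects rapid adoption if doxycycline works, partly because the diagnosis rests on a routine biopsy, so a statement about what the CD138 test can do is likely to be used.

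Even as a prognostic comparison, the two groups are observed under different rules. If every placebo pregnancy counts towards live births per patient, the placebo group gains from longer observation and repeat attempts. That could hide or reverse a real disadvantage of chronic endometritis.

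The 0-4 level in section 12.3 is a smaller matter: it promises an estimate for women who cannot be in the randomised trial.

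**Working it through.** **1. What the comparison estimates.** It is outcome (untreated, low CD138) minus outcome (untreated, high CD138). Assume, for illustration, 56% in screen-negative women and 48% on placebo. The difference is 56 - 48 = +8 points whether doxycycline would have added 0, 8 or 12 points in screen-negative women. The observed quantity does not depend on the treatment effect.

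**2. Size of the follow-up artefact.**

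Inputs from the protocol:
- 24% of women conceive each month, with 80% pregnant by six months (section 12.1.3). Check: 1 - 0.76^6 = 80.7%, which agrees.
- Control rate 48% and intervention rate 56%, a target of 8 points (section 12.1.3).
- Length of follow-up of randomised women. Section 7.11 gives at least 14 months; with recruitment over months 5-30 (Table 6), the first women have about 14 + 26 = 40 months. Table 6 alone, with follow-up ending at month 38, gives 38 - 30 = 8 to 38 - 5 = 33 months. Both ranges are used.

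Assumptions, not in the protocol:
- Success per pregnancy 0.48/0.80 = 60%.
- The same fertility and the same success rate in both groups, so the true difference is zero.
- 3 or 4 months lost after a miscarriage.
- A conception counts if it falls 0 or 3 months before the end of follow-up (reporting lag).
- Follow-up length spread evenly over the range.

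Screen-negative women, first pregnancy within 12 months: (1 - 0.76^12) x 0.60 = 0.963 x 0.60 = 57.8%.

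Placebo women were simulated month by month: geometric waiting time at 24%, success at 60%, and after a loss the gap and then another waiting time.

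| Placebo pregnancies counted | Follow-up | Placebo rate | Gap from 57.8% |
|---|---|---|---|
| All | 14-40 months | about 89-93% | about 31-36 points |
| All | 8-33 months | about 79-86% | about 21-29 points |
| First only | either | about 57-60% | about 2 points or less |

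With first pregnancies only, the placebo rate cannot exceed 60%, so the gap cannot exceed 60.0 - 57.8 = 2.2 points; at short follow-up it can be slightly negative. If both groups share the same 12-month window, both give 57.8% and the artefact is zero.

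Sensitivity: at any one fixed follow-up length (4-month loss, 3-month lag), the all-pregnancy rate runs from 70.0% at 14 months to 97.9% at 40, a gap of 12 to 40 points. If 48% is taken as the success rate per pregnancy, the screen-negative rate is 0.963 x 0.48 = 46.2%, and the averaged all-pregnancy gap is about 24 to 41 points.

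**3. Outcome definition.** Section 3.1 defines on-going pregnancy by crown rump length. Under section 7.9 that measurement is not among the items collected in screen-negative women. Gestation at outcome is collected in both groups.

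**4. The empty level.** Entry at 5 or more cells per 10 mm² (section 6.3) leaves an expected zero randomised women at 0-4. The interaction then has three levels and 2 degrees of freedom, not four levels and 3.

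**The case against.** **The protocol does not say that all placebo pregnancies count.** This stands. Section 3.1.2 counts on-going pregnancy over first pregnancies, and the live-birth item in the section 3.2.1 list is also limited to the first pregnancy after randomisation. On that reading the artefact is about 2 points or less. Placebo pregnancies are recorded in full, so they can be cut to a matching window, and a statistical analysis plan could say so. A reader might infer that the trial is bound to report a large false advantage for placebo; the text does not support that. It leaves the window open, while total live births in section 3.1.3 does count later pregnancies.

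**A valid test of benefit is already planned.** This also stands. Section 12.3 tests treatment by CD138 severity among randomised women, and section 11.1.1 keeps the exact counts for subgroup work. It would be wrong to infer that the trial has no means of studying differential benefit. The fault is that section 3.2.1 assigns that purpose to a comparison that cannot serve it. The section 12.3 test also tells us nothing below 5 cells per 10 mm².

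**The empty level does no harm.** Largely true. It drops out without bias or loss of power, the subgroups are labelled exploratory, and the protocol does not tie them to the section 3.2.1 item. Section 12.3 also omits the area unit, so 0-4 might be a raw count, but the label matches the screening category. It remains a contradiction with section 6.3.

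**Conclusion.** The stated purpose in section 3.2.1 cannot be met with the groups it names. This follows from the text and needs no assumption. As a prognostic comparison the analysis is legitimate, provided that the pregnancy window is matched.

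The cost of leaving the window open ranges from about 2 points or less (first pregnancies only) to about 21 to 36 points (all placebo pregnancies), against a target treatment effect of 8 points. The larger range rests on the assumed 60% success per pregnancy, constant 24% monthly conception, and the assumed gaps and lags. It is an illustration of what the wording permits, not a forecast.

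The 0-4 subgroup level contradicts the entry criterion. The point concerns one secondary item and one exploratory label. The primary analysis, sample size and stopping rules are not affected. It should be corrected because it governs what the trial may conclude about the CD138 test.

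**What to change.** 1. In section 3.2.1, relabel the comparison of screen-negative and placebo women as prognostic. State that benefit is addressed only by the treatment-by-CD138 interaction among randomised women already planned in section 12.3, which informs only women with at least 5 cells per 10 mm². The exact counts kept under section 11.1.1 may be used for it.
2. Limit both groups in that comparison to the first pregnancy conceived within 12 months of a matched start point, analysed per woman, with on-going pregnancy judged by gestation at outcome. A natural start is when each woman is free to try to conceive: after the biopsy result if screen-negative, and after the intervention cycle if on placebo.
3. Delete the 0-4 level from the severity subgroup in section 12.3.

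The cost is wording and a small change to the analysis; no new data are needed. The drawback is that no conclusion can be drawn about doxycycline benefit in screen-negative women, and later placebo pregnancies are left out of this one comparison.

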9.5 Pregnancy review

Participants should be reminded to undergo a urine pregnancy test as soon as their menstrual periods are delayed or a pregnancy is suspected and to contact the site research team immediately.

Communication with participants will then be via telephone until a urine pregnancy test is positive (as per local policy). At each contact a member of the hospital research team will check if participants are trying to conceive, their pregnancy status and pregnancy outcome.

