9.5.2 Women with CE who are randomised

Research staff at site should contact randomised participants every 3 months via telephone, from the treatment completion assessment date, until 6-8 weeks post pregnancy (>24 weeks gestation) or until the trial ends. Research staff should schedule in these calls with participants at each contact.

If a randomised participant confirms pregnancy they should be contacted at the following assessment time points and information should be collected and recorded as specified.

9.6 12 week assessment (+/-2 weeks) – standard practice 12 week scan*

- Pregnancy Confirmation (if not previously collected)
- Ultrasound (standard practice booking scan)
- Crown rump length
- Gestational Age
- Viable pregnancy assessment
- Congenital abnormality
- Concomitant medication review
- Pregnancy complications (if appropriate)
- Collect participant treatment diary (if not previously collected)
- Collect unused medication (if applicable/not previously collected)

9.7 20 – 24 week assessment – standard practice 20-24 week scan*

- Ultrasound
- Viable pregnancy assessment
- Gestational age
- Concomitant medication review
- Pregnancy complications (if appropriate)
- Congenital abnormality

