9.8 Additional visits/scans as per standard practice*

If participant has an additional visit/ultrasound scan between 6 weeks - 20 week please record the following:

- Crown rump length (if recorded)
- Gestational Age
- Viable pregnancy assessment

9.9 End of pregnancy assessment or follow-up $(6 - 8 \text{ weeks post end of pregnancy > 24 weeks gestation})^*$

- Pregnancy outcome assessments
- Concomitant medication review
- Pregnancy complications (if appropriate)
- Postpartum Maternal and infant infections
- Maternal and infant infections 6 weeks post delivery

The end of pregnancy assessment should only be carried out for randomised participants who deliver a baby >24 weeks gestation. This will be the final follow up for the participant.

* These assessments may be conducted by telephone unless there is a clinical need for participants to be seen in hospital.

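### The biochemical class of miscarriage type needs neither a scan nor a gestation limit, so a clinical loss that was never scanned is counted as biochemical

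*Protocol*

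**What the plan says.** Protocol section 3.2.1 lists the secondary outcome as "Type of miscarriage, biochemical¹, gestational sac², fetal³, karyotype of miscarried tissue". Three footnotes define the classes:

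- Footnote 1: "Biochemical – Positive pregnancy test without ultrasound visualisation of pregnancy".
- Footnote 2: "Gestational Sac – Presence of gestational sac on ultrasound without visualisation of fetus".
- Footnote 3: "Presence of fetus on ultrasound with no fetal heart beating".

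None of the three mentions gestation. There is no class for a loss that was never scanned.

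Pregnancy is first picked up remotely. Section 9.5 says "Communication with participants will then be via telephone until a urine pregnancy test is positive", and section 9.5.2 sets the calls at every 3 months. The first scheduled scan is in section 9.6: "12 week assessment (+/-2 weeks) – standard practice 12 week scan". Anything earlier comes under section 9.8, which is conditional: "If participant has an additional visit/ultrasound scan between 6 weeks - 20 week please record the following". Table 5 likewise makes the extra scan depend on clinical need. Section 3.1.2 places nearly all losses early: "As 98% of miscarriages occur before 12 weeks".

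**The concern.** The class a loss receives depends on whether and when a scan was done, as well as on what was lost. Footnote 1 puts two different situations together: a woman who was scanned with nothing seen, and a woman who was never scanned. Most losses are expected before or around the first scheduled scan, so the second situation can arise in ordinary follow-up.

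At stake is the reading of one secondary outcome. If doxycycline reduced only clinical losses, and some of those were never scanned, the biochemical count would fall as well. A reader could then place part of the effect at the wrong stage of pregnancy. The biochemical share would also partly reflect access to early scans at each site.

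**Working it through.** **Step 1. Footnotes set against the scan schedule.**

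| Course of the pregnancy | Class as written |
|---|---|
| Positive test, loss at 8 weeks, no scan | Biochemical (footnote 1) |
| Positive test, scanned, nothing seen, then loss | Biochemical (footnote 1) |
| Sac seen early, later loss with no further scan | Gestational sac, whatever developed in between |
| Heartbeat seen, later scan shows fetus without heartbeat | Fetal (footnote 3) |
| Heartbeat seen, then loss with no later scan of a non-beating fetus | None |

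The first row gives a wrong class and the last row gives no class.

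**Step 2. Is there a planned figure to reproduce?** No. The protocol gives no rate, power or sample size for miscarriage type. The inputs below come from the primary-outcome design in section 12.1.3: 750 women per arm, 80% pregnant by six months, and 48% against 56% ongoing. The 80% is consistent with the stated 24% monthly conception: 1 − 0.76^6 = 0.807.

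**Step 3. Illustration per randomised woman.** Assumptions that are not in the protocol:

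- 60 losses per arm are truly biochemical.
- The whole effect falls on clinical losses.
- The unscanned share u of clinical losses is equal in both arms and lies between 10% and 40%.

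First-pregnancy losses:

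- Placebo: 750 × (0.80 − 0.48) = 240, of which 240 − 60 = 180 are clinical.
- Doxycycline: 750 × (0.80 − 0.56) = 180, of which 180 − 60 = 120 are clinical.

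Recorded biochemical losses are 60 + 180u on placebo and 60 + 120u on doxycycline. The odds ratio uses 750 women per arm.

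| u | Placebo | Doxycycline | Odds ratio (truth 1.00) | 95% CI | Biochemical share of placebo losses (truth 60/240 = 25%) |
|---|---|---|---|---|---|
| 10% | 78 | 72 | (72/678)/(78/672) = 0.91 | 0.65 to 1.28 | 78/240 = 33% |
| 20% | 96 | 84 | (84/666)/(96/654) = 0.86 | 0.63 to 1.17 | 96/240 = 40% |
| 40% | 132 | 108 | (108/642)/(132/618) = 0.79 | 0.60 to 1.04 | 132/240 = 55% |

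**Step 4. The same check per first pregnancy.** Section 3.1.2 also describes ongoing pregnancy as a percentage of first pregnancies. On that reading 52% against 44% are lost, a difference of 8 points. Let b be the true biochemical rate, assumed equal in both arms. Recorded biochemical loss is b + u(0.52 − b) against b + u(0.44 − b), so the spurious difference is u × 8 points.

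| u | Spurious difference | Biochemical risk ratio, b = 10% | Biochemical risk ratio, b = 20% |
|---|---|---|---|
| 10% | 0.8 points | 0.94 | 0.97 |
| 25% | 2.0 points | 0.90 | 0.93 |
| 50% | 4.0 points | 0.87 | 0.89 |

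The risk ratio for clinical loss stays at 0.81 (b = 10%) or 0.75 (b = 20%) whatever u is, because u cancels. The absolute difference in clinical loss shrinks from 8 points to 8(1 − u) points, for example 6.0 at u = 25%.

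**The case against.** **The outcome is minor, and nothing important depends on it.** This stands. The primary outcomes and the interim stopping rules do not use these classes. The mediation analysis in section 12.3 uses conception, early miscarriage and late miscarriage. The laboratory work on mechanism uses CD138+ density, microbiota and stromal-cell measures. A reader might infer that the trial's mechanistic conclusions are compromised, but the protocol does not support that.

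**The size is assumed.** This also stands. Neither the unscanned share nor the number of truly biochemical losses is in the protocol, and the count of 240 against 180 takes one reading of the denominator. All three intervals in step 3 include 1, so even at 40% unscanned the shift alone would not be expected to give a significant result for biochemical loss. With blinded arms and similar scanning, the risk ratio for clinical loss is not biased.

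**Late unscanned losses should be uncommon.** This is fair. Standard scans fall at 12 and 20 to 24 weeks, and second-trimester miscarriage is also listed separately under pregnancy complications.

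**A loss after a heartbeat can be classified.** This is partly right. A reader might infer that every such loss is left out. If a later scan shows the fetus without a heartbeat, footnote 3 applies, so the gap is only the narrower case in the last row of step 1.

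**Ectopic pregnancies might seem to meet footnote 1.** The footnotes qualify a bullet on miscarriage, and ectopic and molar pregnancies have their own bullet. The protocol does not support counting this as an overlap.

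**The details belong in the SAP or eCRF.** Some do, such as which scan decides when there are several. The definition itself is fixed in section 3.2.1 and assigns the wrong class when followed as written, so it is not simply detail left for later.

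**Conclusion.** The point holds as a fault in one secondary-outcome definition. Footnote 1 counts a clinical loss that was never scanned as biochemical, and the three classes leave out a loss that follows a live scan with no later scan of a non-beating fetus. Part of any effect on unscanned clinical losses would be reported as an effect on biochemical losses.

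The size is proportional to the unscanned share, which is unknown. Under the assumptions in step 3 the apparent odds ratio is 0.91 to 0.79 where the truth is 1.00, and the biochemical share on placebo rises from 25% to between 33% and 55%. The per-pregnancy reading gives the same direction with different numbers. If every clinical loss were scanned, the shift would be zero.

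It would be wrong to read this as a threat to the primary result, to early stopping or to the mediation analysis. It deserves correction because the change is cheap and the error lies in the stated rule.

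**What to change.** In section 3.2.1, classify each miscarriage by the most advanced structure seen on any scan in that pregnancy, in four classes:

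- (a) no scan done, type unknown;
- (b) scanned, nothing seen (biochemical);
- (c) gestational sac seen, no fetus seen;
- (d) fetus seen, with or without an earlier heartbeat.

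Every miscarriage falls into exactly one class, and the rule settles what to do with several scans. Record gestation at loss by dates. Report class (a) separately by gestation and do not merge it into biochemical. No gestation cut-off is proposed, because the protocol gives no basis for one.

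The cost is wording and one or two eCRF fields: gestation at loss and, if not already captured, the most advanced structure seen. Section 9.8 lists crown rump length, gestational age and viability, but not this item. The biochemical count will be smaller, because very early losses that were never scanned also move to class (a). A sac seen early and followed by an unscanned loss stays in class (c), so the recorded gestation is needed to interpret it. No extra scans or visits are required.
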